3.4.2.2 Pause Rules

Study pause rules will be continuously monitored during all phases of the study by the investigators, study medical monitor, Sponsor medical lead, IST, and SMC (as warranted). If the investigator, study medical monitor, Sponsor medical lead, IST, or SMC request that the study be paused due to a safety concern, further study vaccine administration in the affected cohort and at higher dose levels will be suspended, but all other planned procedures relating to safety, reactogenicity, and immunogenicity assessments will continue as described in the protocol.

The occurrence of any of the events listed in Table 2, regardless of dosing group, will result in immediate suspension of dosing and enrollment in the cohort. An unscheduled meeting of the SMC will be convened to assess specific data concerns and to make recommendations.

The Sponsor will notify the Center for Biologics Evaluation and Research within 48 hours in the event of a study pause.

Table 2: Pause Rules Based on the Occurrence of a Single Adverse Event and Adjudicated by the SMC

Pause Rule	Adverse Event	Number of Participants per Dose Cohort
1	Any serious adverse event that cannot be reasonably attributed to a cause other than vaccination	≥ 1
2	Any Grade 4 adverse event that cannot be reasonably attributed to a cause other than vaccination	≥ 1
3	Any systemic immediate hypersensitivity reaction within 60 minutes after the study vaccination	≥ 1

Abbreviation: SMC = Safety Monitoring Committee.

Table 3 summarizes safety events that will pause study dosing based on defined threshold levels, which are aggregate incidences relative to the number of exposed participants within a dosing group. An unblinded statistician may be consulted to determine if a pause rule has been met.

Table 3: Pause Rules Based on the Occurrence of Adverse Events in a Proportion of Participants

Pause Rule	Adverse Event	Number of Participants per Dose Cohort ^a	
4	Any Grade 3 solicited local adverse event lasting more than 24 hours in an mRNA-1893 cohort ^b within the 7-day (Days 1-8) post-vaccination period	≥ 20% and ≥ 2 participants/group	
5	Any Grade 3 solicited general adverse event lasting more than 24 hours in an mRNA-1893 cohort ^b that cannot be reasonably attributed to a cause other than vaccination, within the 7-day (Days 1-8) post-vaccination period	\geq 20% and \geq 2 participants/group	

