3.5.6 Solicited Safety Measurements

The term "reactogenicity" refers to selected signs and symptoms (AEs) occurring after vaccine administration that the participants are systemically asked to record. Participants will record such occurrences in a diary card (Section 3.5.2) on the day of each vaccine administration and for the 6 days after vaccine administration. Participants will be instructed to call or return to the clinic within 24 hours if a reactogenicity score reaches Grade 3 or greater during the first 6 days after vaccination.

The following AEs are included on the diary card:

- Solicited local AEs:
 - Injection site pain
 - Injection site erythema
 - Injection site induration/swelling
- Solicited systemic AEs:
 - Body temperature (oral)
 - Generalized myalgia (muscle ache or pain)
 - Generalized arthralgia (joint ache or pain)
 - Headache
 - Fatigue/malaise (unusual tiredness)
 - Nausea/vomiting
 - Chills
 - Rash

Appropriate reactogenicity measurements will be taken using the tools provided by Sponsor (oral thermometer and measuring device; Section 3.5.2). The investigator will later review, confirm, and grade reactogenicity according to the Guidance for Industry: Toxicity grading scale for healthy adult and adolescent volunteers enrolled in preventative vaccine clinical trials (DHHS 2007; Table 6).

In case of any rash episode observed within 6 days after study vaccination, the participants will be instructed to contact the study site within 24 hours. During subject evaluation, the investigator should categorize the rash as one of the following:

- Rash no longer present and history not consistent with urticaria.
- Rash no longer present but history is consistent with urticaria.
- Rash present but clinical findings are not consistent with urticaria. Alternative diagnosis should be specified as an AE.
- Rash present and clinical findings consistent with urticaria.

If a solicited local or systemic reactogenicity AE continues beyond 7 days after vaccine administration, it will also be recorded as an AE in the eCRF from 8 days after vaccination until the AE has resolved or stabilized (Section 3.5.7.1.1).

Other solicited reactions will include the following:

- Use of analgesics and/or antipyretics will be recorded as absent or present, and participant will indicate if use was for treatment or prophylaxis.

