3.6 Statistical Analysis Plans

3.6.1 Primary Endpoints

The following are the primary endpoints of the study:

• Frequency and grade of each solicited local and systemic reactogenicity AE during a 7-day follow-up period after each vaccination

- Frequency and grade of any unsolicited AEs during the 28-day follow-up period after each vaccination
- Frequency of any MAAE, SAE, and AESI from Day 1 to the EOS Visit at Month 13

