Source: Guidance for industry – Toxicity grading scale for heathy adult and adolescent volunteers enrolled in preventative vaccine clinical trials; Tables for clinical abnormalities (DHHS 2007).

^{*} Participant should be at rest for all vital sign measurements.

^{**} When resting heart rate is between 60 – 100 beats per minute. Use clinical judgment when characterizing bradycardia among some healthy participant populations, for example, conditioned athletes.

Systemic (General)	Mild (Grade 1)	Moderate (Grade 2)	Severe (Grade 3)	Potentially Life-threatening (Grade 4)
Fever (°C) * (°F) *	38.0 – 38.4 100.4 – 101.1	38.5 – 38.9 101.2 – 102.0	39.0 – 40 102.1 – 104	> 40 > 104
Nausea/vomiting	No interference with activity or 1 to 2 episodes/ 24 hours	Some interference with activity or > 2 episodes/ 24 hours	Prevents daily activity, requires outpatient IV hydration	ER visit or hospitalization for hypotensive shock
Diarrhea	2 – 3 loose stools or < 400 g/ 24 hours	4 – 5 stools or 400 – 800 g/ 24 hours	6 or more watery stools or > 800 g/ 24 hours or requires outpatient IV hydration	ER visit or hospitalization
Headache	No interference with activity	Repeated use of non- narcotic pain reliever > 24 hours or some interference with activity	Significant; any use of narcotic pain reliever or prevents daily activity	ER visit or hospitalization
Fatigue/Malaise (unusual tiredness)	No interference with activity	Some interference with activity	Significant; prevents daily activity	ER visit or hospitalization
Generalized myalgia (muscle ache or pain)	No interference with activity	Some interference with activity	Significant; prevents daily activity	ER visit or hospitalization
Generalized arthralgia (joint ache or pain)	No interference with activity	Some interference with activity not requiring medical intervention	Prevents daily activity and requires medical intervention	ER visit or hospitalization

Abbreviations: ER = emergency room; IV = intravenous.

^{*} Oral temperature; no recent hot or cold beverages or smoking.

Sources: Guidance for industry – Toxicity grading scale for heathy adult and adolescent volunteers enrolled in preventative vaccine clinical trials; Tables for clinical abnormalities (DHHS 2007). Division of AIDS Grading the Severity of Adult and Pediatric Adverse Events (DHHS 2014).

Table 7: Tables for Laboratory Abnormalities

Serum Chemistry*	Mild (Grade 1)	Moderate (Grade 2)	Severe (Grade 3)	Potentially Life-threatening (Grade 4)**

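### The Table 6 arthralgia row leaves two combinations without a grade, so disabling joint pain may be under-graded or inconsistently graded in the primary solicited endpoint and may not count toward pause rule 5

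*Protocol*

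**What the plan says.** Protocol Appendix 3, Table 6 (systemic part) grades generalized arthralgia on two features, activity limitation and medical intervention:

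- Grade 1: activity not affected.
- Grade 2: "Some interference with activity not requiring medical intervention".
- Grade 3: "Prevents daily activity and requires medical intervention".
- Grade 4: emergency room visit or hospitalization.

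The fatigue and myalgia rows define Grade 3 as "Significant; prevents daily activity", with no intervention condition. Headache reaches Grade 3 through narcotic use or stopped activity, either being enough. Nausea/vomiting is the other solicited systemic row that names an intervention beside function at Grade 3: "Prevents daily activity, requires outpatient IV hydration".

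Protocol 3.5.6 lists arthralgia as a solicited systemic reaction. Protocol 3.6.1 makes the first primary endpoint "Frequency and grade of each solicited local and systemic reactogenicity AE during a 7-day follow-up period after each vaccination". Protocol 3.4.2.2, Table 3, starts pause rule 5 from "Any Grade 3 solicited general adverse event lasting more than 24 hours", with a threshold of at least 20% and at least 2 participants. For the first 5 participants the threshold is 2 with the same event.

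On who grades, Protocol 3.5.6 says: "The investigator will later review, confirm, and grade reactogenicity according to the Guidance for Industry". SAP 7.6.1 derives grades by program only for erythema, swelling and fever, and leaves the rest to the investigator.

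**The concern.** A grading row should place every possible event in exactly one grade. This one does not. An investigator facing joint pain that stops daily activity, handled without medical intervention, has something worse than Grade 2 that does not meet Grade 3. The same disability reported as muscle pain is Grade 3.

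Three Grade 3 uses depend on how that gap is filled: the Grade 3 row of a primary endpoint tabulated by grade, the numerator of pause rule 5 in a first-in-human dose escalation, and the instruction to contact the site within 24 hours (Protocol 3.1 and 3.5.6). If investigators fill it differently across sites or cohorts, a difference between dose groups in Grade 3 arthralgia could partly reflect the grader.

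**Working it through.** **Step 1. Cross the two features in the arthralgia row** (leaving aside Grade 4).

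| Activity | No medical intervention | Medical intervention |
|---|---|---|
| Not affected | Grade 1 | Grade 1 |
| Partly limited | Grade 2 | no grade |
| Stopped | no grade | Grade 3 |

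Two of the six combinations have no grade.

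**Step 2. Look for text that closes the gap.** The mild/moderate/severe definitions in Protocol 3.5.7.4 apply to unsolicited events not listed in the toxicity scale. The SAP rule that counts missing severity as Grade 3 stands in the unsolicited-event summaries (7.6.2.2 and 7.6.2.3). Neither reaches a solicited reaction that is listed in the scale. Neither document defines medical intervention.

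**Step 3. Check the plan's own probability statement.** Protocol 3.6.4 gives the chance of at least one event in 24 vaccinees. 1 − 0.90^24 = 0.9202 and 1 − 0.95^24 = 0.7080, matching the stated 92% and 70.8%. These figures are unaffected by this point.

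**Step 4. Pause threshold.** 20% of 24 is 4.8, so rule 5 needs 5 vaccinees: 5/24 = 20.8%.

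**Step 5. Illustration with assumed counts.** Suppose 5 of 24 vaccinees have arthralgia that stops activity for more than 24 hours, with no medical intervention and no other Grade 3 systemic event. The literal row gives 0/24 at Grade 3; the myalgia criterion gives 5/24. In the first 5 participants, 2 such cases count as 0 rather than 2.

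**Step 6. Range.** Let p be the true rate of activity-stopping arthralgia lasting more than 24 hours, and f the share that also needs medical intervention. Both are assumptions. Take ungraded events as not Grade 3 and assume no other Grade 3 systemic event. The chance of meeting rule 5 is then P(X ≥ 5), with X ~ Binomial(24, p·f) on the literal row and Binomial(24, p) on the myalgia criterion.

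| p | Literal, f = 0.25 | Literal, f = 0.50 | Literal, f = 1 | Myalgia criterion |
|---|---|---|---|---|
| 0.10 | 0.0003 | 0.006 | 0.085 | 0.085 |
| 0.20 | 0.006 | 0.085 | 0.540 | 0.540 |
| 0.30 | 0.030 | 0.287 | 0.889 | 0.889 |
| 0.40 | 0.085 | 0.540 | 0.987 | 0.987 |

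At p = 0.30 and f = 0.25, the expected Grade 3 count is 24 × 0.075 = 1.8 against 24 × 0.30 = 7.2. If the threshold is read as 6 of all 30 in the cohort, with events only in the 24 vaccinees, the probabilities at the same p and f are 0.007 and 0.771. For the first-5 check, with 4 vaccinees and an event-free placebo recipient, P(at least 2 of 4) is 0.030 against 0.348.

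**The case against.** A reader might infer that these reactions disappear from the primary endpoint. The documents do not support that. The investigator assigns a grade to each reaction, and nothing says an event between two grades is left blank or dropped. SAP 7.6.1 lists every solicited reaction and tabulates an any-grade row alongside the separate grades. What can be lost is the place in the Grade 3 row.

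A reader might also infer that the pause safeguard fails. That is too strong as well. A participant with concurrent Grade 3 myalgia, fatigue or headache may still count toward rule 5; Table 3 does not say whether counting is by event term or by any systemic event. Protocol 3.4.2.2 lets the investigator, study medical monitor, Sponsor medical lead, IST or SMC request a pause for a safety concern. The IST reviews all available safety data before escalation (3.4.2.1), not only Grade 3 counts. These provisions soften the effect, but they do not repair a pre-specified numerical rule or a table of grades.

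The size also turns on an undefined term. Protocol 3.4.8.2 expects analgesics and antipyretics for symptom relief. An investigator who counts these as medical intervention would place many such cases in Grade 3, and the difference shrinks toward zero. This stands as a limit on the magnitude, and it is itself a reason to define the term.

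Finally, requiring both function and treatment is not foreign to the protocol: the nausea/vomiting row and the severe category in 3.5.7.4 do something similar. So the documents do not show that the myalgia wording is the correct benchmark. The systemic part of Table 6 also cites two outside scales that cannot be consulted here. Neither point fills the two empty combinations in the row as printed.

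**Conclusion.** The gap is real on the face of Table 6. The likely consequence is under-grading or inconsistent grading of disabling arthralgia in the Grade 3 row of the primary solicited endpoint. Such events may also fail to count toward pause rule 5 or to prompt the Grade 3 site contact. Complete loss from the endpoint is not supported.

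The effect ranges from nothing, when every such case needs intervention, to a large fall in the chance of meeting rule 5 when few do. It depends on three things the documents do not give: how often activity-stopping arthralgia occurs, how often it needs medical intervention, and how often it occurs without another Grade 3 systemic reaction. The 5 of 24 example is a labelled assumption and not a forecast. The point deserves correction because the row feeds a primary endpoint and a pre-specified pause rule, and clarifying it is cheap.

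**What to change.** - Reconcile the arthralgia row with the other functional rows of Table 6, checking nausea/vomiting at the same time, so that every combination of activity limitation and medical intervention falls in exactly one grade. The sponsor's clinical team sets the cut-points.
- State what counts as medical intervention, including whether analgesic or antipyretic use does.
- Use the reconciled row for investigator grading under SAP 7.6.1 and for pause rule 5.
- Regrade arthralgia already recorded only where the source supports it, by staff blinded to treatment, and label the result a sensitivity analysis. Two limits apply. Diary cards are the only source for solicited reactions and cannot be changed after delivery (Protocol 3.5.2). Selected Sponsor staff are unblinded at each cohort's Day 57 interim analysis (Protocol 3.4.5), so regrading by them would be open to challenge.

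The cost is a one-row amendment with a matching SAP reference and some limited regrading work. Reported Grade 3 counts may rise slightly.

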6.4 Appendix 4: List of Hepatotoxic Drugs

Cardiovascular

- Amiodarone
- Atorvastatin
- Hydralazine
- Methyldopa
- Quinidine
- Simvastatin
- Ticlopidine

Antimicrobial

- Amoxicillin-clavulanate
- Didanosine
- Efavirenz
- Erythromycin
- Flucloxacillin
- Interferon alpha/Peginterferon
- Isoniazid
- Ketoconazole
- Minocycline
- Nevirapine
- Nitrofurantoin
- Pyrazinamide
- Rifampin
- Sulfamethoxazole/Trimethoprim
- Sulfasalazine
- Sulfonamides
- Telithromycin

Antineoplastic/Immunosuppressives

- Azathioprine/6-Mercaptopurine
- Busulfan
- Floxuridine
- Flutamide
- Gold salts
- Infliximab
- Interferon beta
- Methotrexate
- Propylthiouracil
- Thioguanine

Neurologic

- Carbamazepine
- Chlorpromazine
- Dantrolene
- Disulfiram
- Phenytoin
- Valproate

Nonsteroidal antiinflammatory

- Diclofenac
- Ibuprofen
- Nimesulide
- Sulindac

Miscellaneous

- Allopurinol
- Anabolic steroids
- Contraceptives
- Halothane

Source: Björnsson 2016

| 8 | CH | ANGES AND CLARIFICATIONS FROM PLANNED ANALYSES IN | |
| | PRO | OTOCOL | . 31 |
| 9 | REI | FERENCES | , 31 |
| 10 | LIS | T OF APPENDICES | . 32 |

| otocol mRNA-1893-P101 | Date Issued: 25May2021 |
|--|--------------------------|
| 10.1 APPENDIX A ANALYSIS VISIT WINDOWS FOR SAFETY AND IMMUNO | OGENICITY ANALYSIS 32 |
| $10.2~{ m AppendixBS}$ Standards for Safety and Immunogenicity Var | RIABLE DISPLAY IN TFLS34 |
| 10.3 APPENDIX C IMPUTATION RULES FOR MISSING OR PARTIAL MEDIC | ATION DATES 34 |
| 10.4 APPENDIX D: IMPUTATION RULES FOR MISSING AE DATES | 35 |
| 10.5 APPENDIX E: SCHEDULE OF EVENTS | 36 |
| 10.6 APPENDIX F: IMMUNOGENICITY ASSESSMENTS | 36 |

Protocol mRNA-1893-P101

Document History

| Version | Date | Changes |
|---------|-------------|--|
| 1.0 | 24Oct2019 | Original Version |
| 2.0 | 18Mar2020 | Removed references to 1:10 for the LLOQ in Section 4.2, and Section 4.3 |
| 3.0 | 20 May 2021 | Visit window for Immunogenicity for month 13 changed to [343, 385] |
| | | Changed GMT to GMC |
| | | Changed of "bAb titer from below the LLOQ" to "a change of bAb concentration from below the LLOQ" |
| | | Changed "2-fold or 4-fold increase in bAb titers" to "2-fold or 4-fold increase in bAb concentration |

List of Abbreviations

| Abbreviation | Definition | | |
|--------------|--|--|--|
| AE | adverse event | | |
| AESI | adverse event of special interest | | |
| AR | adverse reaction | | |
| bAb | serum binding antibody | | |
| BMI | body mass index | | |
| CI | confidence interval | | |
| eCRF | electronic case report form | | |
| ELISA | enzyme-linked immunosorbent assay | | |
| EOS | end of study | | |
| GMT | geometric mean titer | | |
| IgG | immunoglobulin G | | |
| IgM | immunoglobulin M | | |
| IRB | Internal Review Board | | |
| IRT | Interactive Response Technology | | |
| IST | Internal safety team | | |
| ITT | intent-to-treat | | |
| LLOQ | lower limit of quantification | | |
| MAAE | medically attended adverse event | | |
| MedDRA | Medical Dictionary for Regulatory Activities | | |
| MN | microneutralization assay | | |
| nAb | serum neutralizing antibody | | |
| PP | per-protocol | | |
| PRNT | plaque reduction neutralization test | | |

Protocol mRNA-1893-P101

| Abbreviation | Definition | |
|--------------|------------------------------------|--|
| PT | preferred term | |
| RVNT | reporter virus neutralization test | |
| SAE | serious adverse event | |
| SAP | statistical analysis plan | |
| SAS | Statistical Analysis System | |
| SD | standard deviation | |
| SOC | system organ class | |
| TEAE | treatment-emergent adverse event | |
| ULOQ | upper limit of quantification | |
| ZIKV | Zika virus | |

Protocol mRNA-1893-P101

1 Administrative Structure

This study is being conducted under the sponsorship of ModernaTX, Inc. The safety and immunogenicity statistical analyses are being performed under contract with PPD in collaboration with ModernaTX, Inc.

2 Introduction

This statistical analysis plan (SAP), which describes the planned analyses for Study mRNA-1893-P101, is based on the most recent approved clinical study protocol, Version 2.0, dated 17 July 2019 and the most recent approved electronic case report form (eCRF) Version 5.0, dated 24 July 2019.

In addition to the information presented in the statistical analysis plans section of the protocol (Section 3.6) which provides the principal features of analyses for this study, this SAP provides statistical analysis details/data derivations. It also documents modifications or additions to the analysis plan that are not "principal" in nature and information that was not available at the time of protocol finalization.

PPD Biostatistics and Programming team, designee of Moderna Biostatistics and Programming department, will perform the statistical analysis of the safety, reactogenicity, and immunogenicity data; Statistical Analysis System (SAS; Version 9.4 or higher) will be used to generate all statistical outputs (tables, figures, listings, and datasets).

The SAP will be finalized and approved prior to the first interim analysis clinical database lock and treatment unblinding for the study. If the statistical analysis methods in this SAP differ from the methods described in the protocol, the SAP will prevail.

3 Study Objectives

3.1 Primary Objective

The primary objective of the study is to evaluate the safety, tolerability, and reactogenicity of a 2-dose vaccination schedule of mRNA-1893 Zika vaccine, given 28 days apart, across a range of dose levels in flavivirus-seronegative and flavivirus-seropositive participants compared with placebo.

Protocol mRNA-1893-P101

3.2 Secondary Objective

The secondary objective of the study is to evaluate the immunogenicity of a 2-dose vaccination schedule of mRNA-1893 Zika vaccine, given 28 days apart as measured by Zika virus (ZIKV)-specific neutralization assay (Plaque Reduction Neutralization Test [PRNT]).

3.3 Exploratory Objectives

The exploratory objectives of the study are the following:

- 1. To evaluate the immunogenicity of a 2-dose vaccination schedule of mRNA-1893 Zika vaccine, given 28 days apart, as measured by enzyme-linked immunoabsorbent assay (ELISA) and additional neutralization assays.
- 2. To assess the occurrence of flavivirus infection throughout the course of participation in the trial.

4 Study Endpoints

4.1 Primary Endpoints

The primary endpoints for the study are the following:

- Frequency and grade of each solicited local and systemic reactogenicity adverse reaction (AR) during a 7-day follow-up period after each vaccination
- Frequency and grade of any unsolicited adverse events (AEs) during the 28-day follow-up period after each vaccination
- Frequency of any medically attended adverse event (MAAE), serious adverse event (SAE), and adverse event of special interest (AESI) from Day 1 to the end of study (EOS) Visit at Month 13

Other safety assessments include clinical laboratory test results (hematology, serum chemistry, and coagulation); vital sign measurements; and physical examination findings.

4.2 Secondary Endpoints

The secondary endpoints for the study are the following:

• Geometric mean titer (GMT) of neutralizing antibody (nAb) against ZIKV at Day 1, Day 29, Day 57, Month 7, and Month 13 as measured by PRNT

Protocol mRNA-1893-P101

• GMT of nAb in initially seronegative participants against ZIKV at Day 1, Day 29, Day 57, Month 7, and Month 13 as measured by PRNT

- GMT of nAb in initially seropositive participants against ZIKV at Day 1, Day 29, Day 57, Month 7, and Month 13 as measured by PRNT
- Percentage of participants who seroconverted from Day 1 (baseline) to Day 29, from Day 1 to Day 57, from Day 1 to Month 7, and from Day 1 to Month 13. A seroconversion is defined as a change of PRNT from below the lower limit of quantification (LLOQ) to a PRNT equal to or above LLOQ, or an increase of at least 4-foldin participants with pre-existing PRNT titers.
- Proportion of initially seronegative participants with a seroresponse at Day 29, Day 57, Month 7, and Month 13 as measured by PRNT. A seroresponse is defined as a change of PRNT from below the LLOQ to greater than or equal to the LLOQ.
- Proportion of initially seropositive participants with a 2-fold or 4-fold increase in nAb titers as compared with baseline as measured by PRNT

